9.4.16 SpondyloArthritis Research Consortium of Canada (SPARCC) scores

SPARCC scores for spine and sacroiliac (SI) joints are calculated by adding up the dichotomous outcomes from evaluations of the presence, depth and intensity of bone marrow edema lesions of the spine and SI joints, respectively.

SPARCC Assessment of Spine Scoring

In the SPARCC assessment of the MRI of the spine, the entire spine is evaluated for active inflammation (bone marrow edema) using the STIR image sequence. 23 discovertebral units (DVUs) are assessed by each reviewer per subject and timepoint, and the six most severely affected DVUs are selected by each reviewer and used to calculate the MRI Spine SPARCC score. For each of the six DVUs, 3 consecutive sagittal slices are assessed in four quadrants in order to evaluate the extent of inflammation in all three dimensions.

1. Each quadrant is scored for presence of increased signal on STIR
 - 1 = increased signal
 - 0 = normal signal

2. Presence, on each of the sagittal slices, of a lesion exhibiting high signal intensity (comparable to cerebrospinal fluid) in any disco-vertebral unit is given an additional score of 1.
3. Slices that included a lesion demonstrating continuous increased signal of depth ≥ 1 cm extending from the endplate are to be scored as +1 per slice.

The maximum possible score for any individual slice is 6, with a maximum score for all 6 discovertebral units being 108.

SPARCC Assessment of SI Joint Scoring

Scoring is conducted on 6 consecutive slices of the STIR image sequence. All lesions within the iliac bone and within the sacrum up to the sacral foramina are to be scored. The SI joint is divided into 4 quadrants: upper iliac, lower iliac, upper sacral and lower sacral. Each consecutive slice is scored separately for the right and left joint in all four quadrants as follows:

1. Each quadrant is scored for presence of increased signal on STIR
 - 1 = increased signal
 - 0 = normal signal
2. Joints that include a lesion exhibiting intense signal on the STIR sequence are scored as +1 per slice.
3. Joints that included a lesion demonstrating continuous increased signal of depth ≥ 1 cm from the articular surface are to be scored as +1 per slice.

The maximum possible score for any individual slice is 12, with a maximum score for all 6 slices being 72.

Adjudication by a third reader

Should adjudication be required for a given case, another reviewer, different from the reviewers who performed primary assessments will make a third, independent assessment. There will be a single dedicated adjudicator performing all adjudication reads.

The 2 closest of the 3 readings (2 primary readers and adjudicator) will determine the final score.

9.4.17 Modified Stoke Ankylosing Spondylitis Spine Score (mSASSS)

The modified Stoke Ankylosing Spondylitis Spine Score (mSASSS) is a scoring method that measure radiographic progression in the spine of patients with ankylosing spondylitis. The mSASSS has a range of 0 to 72, which is derived from scoring the anterior site of the lumbar spine from the lower border of T12 to the upper border of S1 and the anterior site of the cervical spine from the lower border of C2 to the upper border of T1 as either 0 (normal), 1 (erosion, sclerosis, or squaring), 2 (syndesmophyte), 3 (bridging syndesmophyte), or NA vertebral body not evaluable.

Selection of Scores and Adjudication of mSASSS

X-ray of spinal films will be read by two independent readers who are blinded to both treatment and time point. The blinded data read will be performed to compare radiographic progression (from Baseline to the follow-up timepoint, e.g., Year 2).

Adjudication trigger: If the follow-up mSASSS progression scores of read 1 and read 2 differ by ■ mSASSS points for a given subject, a third independent reader (adjudicator) will perform an adjudication read and score that subject. The 2 closest of the 3 readings (2 primary reader and adjudicator) will determine the final score.

Handling of missing joints in the mSASSS

If a score at any location (vertebral unit, VU) is missing, the method described below will be used for deriving mSASSS.

- If the score for a location is missing at Baseline, this location will not contribute to the calculation of mSASSS for this subject at any visit within the reading session (even if the score for this location is available at postbaseline visits).
- If the score for a location is missing at all post-baseline visits within a reading session, this location will not contribute to the calculation of mSASSS for this subject at any visit within the reading session (even if the score for this location is available at Baseline).
- If the score for a location is available at Baseline and at least one postbaseline visit, missing scores for this location at any other post-baseline visit will be imputed assuming no progression from the previous time point with available score.

9.4.18 Other Efficacy Variables

- Patient's Global Assessment of Disease Activity NRS [0 - 10]
 - No activity is indicated by 0 and severe activity by 10.
- Patient's Assessment of Total Back Pain NRS [0 - 10]
 - No pain is indicated by 0 and most severe pain by 10.
- Physician's Global Assessment of Disease Activity NRS [0 - 10]
 - No activity is indicated by 0 and severe activity by 10.
- Patient's Assessment of Nocturnal Back Pain NRS [0 - 10]
 - No pain is indicated by 0 and worst possible pain by 10.
- Patient's Global Assessment of Pain NRS [0 - 10]
 - No pain is indicated by 0 and severe pain by 10.

10.0 Safety Analysis

10.1 General Considerations

Safety analyses will be carried out using the Safety Analysis Set. There are two sets of planned safety analysis: safety analysis for Period 1, and long-term safety analysis.

Safety Analysis for Period 1

Standard safety analysis by the "as treated" treatment groups of Upadacitinib 15 mg QD and placebo group will be performed on safety data in Period 1. No protocol-defined treatment switching will occur prior to these time points.

The standard safety analyses will include reporting of adverse events (AEs), laboratory, and vital signs measurements. Frequency tables of subjects with treatment-emergent adverse events (TEAEs) by system organ class (SOC) and by preferred term (PT) as in the Medical Dictionary for Regulatory Activities (MedDRA) dictionary will be provided by treatment group. All continuous laboratory parameters and vital signs variables at each visit will be summarized by "as treated" treatment group. Frequency tables of subjects meeting criteria for potentially clinically significant vital sign values and for potentially clinically significant laboratory values will be provided by treatment group. Missing safety data will not be imputed.

Long-Term Safety Analysis

Long-term safety analyses that account for protocol-defined treatment switching include reporting of AE rate adjusted by cumulative exposure, descriptive summary in laboratory parameters and vital sign variables, and rate of potentially clinically significant laboratory and vital signs values. The treatment-emergent adverse event (TEAE) rate per 100 patient-years of exposure will be presented by actual treatment received at the time of AE (as described in Section 10.2.2). Listing of subjects with TEAEs by SOC and PT will be provided. All continuous laboratory parameters and vital signs variables at each visit will be summarized by "as treated" treatment group sequences defined as follows. Frequency tables and listings of subjects meeting criteria for potentially clinically significant vital sign values and for potentially clinically significant laboratory values will be provided by actual treatment received at the time of event. Missing safety data will not be imputed.

"As treated" treatment group sequences:

1. Placebo → Upadacitinib 15 mg QD
2. Upadacitinib 15 mg QD → Upadacitinib 15 mg QD

10.2 Analysis of Adverse Events

A treatment-emergent Adverse Event (TEAE) is defined as an adverse event with an onset date that is after the first dose of study drug, and no more than 30 days of the drug after the last dose of study drug.

Events where the onset date is the same as the study drug start date are assumed to be treatment-emergent, unless the study drug start time and the adverse event start time are collected and the adverse event start time is prior to the study drug start time. If an incomplete onset date was collected for an adverse event, the event will be assumed to be treatment-emergent unless there is other evidence that confirms that the event was not treatment-emergent (e.g., the event end date was prior to the study drug start date).

Adverse event data will be presented by SOC and PTs using MedDRA Version 19.1 or most up to date version. All adverse event tables will be sorted in alphabetical order by SOC and PT and descending percentages for each treatment group.

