8.1.5.2 Analysis of Adverse Events

8.1.5.2.1 Treatment-Emergent Adverse Events (TEAE)

AEs will be coded using MedDRA. A TEAE is defined as AE that began or worsened in severity after initiation of study drug.

AEs starting more than 30 days following the last dose of study drug will not be included in summaries of TEAEs.

As a general safety summary, the number and percentage of subjects experiencing TEAEs will be summarized for each treatment group for the following AE categories:

- All AEs;
- All severe AEs;
- All reasonably possibly related AEs;
- All SAEs;
- Frequent AEs (reported in 5% of subjects or more in any treatment group);
- Frequent reasonably possibly related AEs (reported in 5% of subjects or more in any treatment group);
- Discontinuations due to AEs;
- Death.

Additional AEs may be considered for tabulation/summary based on recommendations from the TA MD and Pharmacovigilance and Patient Safety as deemed appropriate.

TEAEs will be summarized and presented by SOC and PTs using MedDRA. The SOC will be presented in alphabetical order, and the PTs will be presented in alphabetical order within each SOC.

TEAE will also be summarized by maximum severity and by maximum relationship.

The AEs of special interest (including but not limited to infection, opportunistic infection, herpes zoster, TB, gastrointestinal perforations, malignancies, MACE, renal dysfunction, anemia, increased CPK, and drug-related hepatic disorders) will be summarized.

All AEs leading to discontinuation of study drug will be presented in listing format. A listing by treatment group of TEAEs grouped by MedDRA SOC and PT with subject identification numbers will be generated.

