4.5 Long-term Analysis and Database Locks

A Week 104 analysis will be conducted after all subjects have completed Week 104 or have prematurely discontinued prior to Week 104. This will be the final efficacy analysis for the entire study. Safety analysis will include data collected up to Week 104 or premature discontinuation for every subject.

At the final database lock when the study completes, updated long-term safety analysis will be conducted.

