8.0 Study Drug Exposure and Compliance

8.1 Study Drug Exposure

The duration of exposure to study drug will be summarized for the safety analysis set by the randomized treatment groups (placebo group vs Upadacitinib 15 mg QD) in Period 1. For long term, the duration of exposure to study drug will be summarized for the safety analysis set only for the Any Upadacitinib 15 mg QD group, which includes Upadacitinib

15 mg QD exposure from subjects starting on Upadacitinib 15 mg QD and subjects switching from placebo to Upadacitinib 15 mg QD.

Exposure to upadacitinib and placebo is defined as last dose date minus first dose date plus 1 day.

The duration of exposure to study drug will be summarized for each group as specified above, with the number of subjects, mean, standard deviation, median, minimum and maximum values. In addition, the number and percentage of subjects exposed to study drug will be summarized for the following cumulative duration intervals.

- ≥ 2 weeks
- ≥ 1 month
- ≥ 3 months
- ≥ 6 months
- ≥ 9 months
- ≥ 12 months
- ≥ 18 months
- ≥ 2 years

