10.2.2 Analysis of Long-Term Adverse Event

Long-term adverse events will be analyzed using event rates adjusted by cumulative exposure and will be based on the actual treatment received at the time of AE occurrence. According to the study design, randomized placebo subjects switch to Upadacitinib 15 mg

QD when entering Period 2, this analysis will be reported for Any Upadacitinib 15 mg QD subjects. The Any Upadacitinib 15 mg QD treatment group is defined as subjects who receive at least one dose of Upadacitinib 15 mg QD at any time during the study.

This includes AEs occurred under Upadacitinib 15 mg QD exposure from subjects starting on Upadacitinib 15 mg QD and subjects switching from placebo to Upadacitinib 15 mg QD.

Exposure-Adjusted Event Rate (EAER)

To adjust for potentially different follow-up time between treatment groups, EAER will be provided. For the purpose of event rate calculation, the numerator will be the total number of AEs reported for the event (i.e., a subject can contribute more than one event to the numerator) and the denominator will be the total exposure time among subjects under the treatment group. The number of AEs reported (numerator), the total number of years of study drug exposure (denominator), and the exposure-adjusted AE event rate per 100 patient-years calculated as $([\text{numerator (days)}/\text{denominator}])/365.25 \cdot 100$ will be presented for each treatment group. The EAER will be the main approach to evaluate AEs in the long-term analysis.

In addition, the exposure-adjusted incidence rate (censored at first event) will be conducted for AESI endpoints as deemed appropriate for long-term analysis.

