10.2.2.1 Overview of Adverse Events Rates per 100 Patient-Years of Study Drug Exposure

An overview of AEs per 100 patient-years of study exposure will be presented for Any Upadacitinib 15 mg QD for the following AE categories.

- All TEAEs
- Treatment-emergent serious adverse events (SAEs)
- Treatment-emergent severe adverse events
- TEAEs reasonably possibly related to study drug
- TEAEs of special interest

- TEAEs leading to discontinuation of study drug
- TEAE leading to death

The number of TEAEs reported, the total number of years of study drug exposure, and the TEAE rate per 100 patient-years will be presented for Any Upadacitinib 15 mg QD group.

Additional AEs may be considered for tabulation/summary based on recommendations from Clinical and Safety as deemed appropriate.

For TEAE of special interest, the point estimate and 95% CI (using normal approximation) will be provided for the Any Upadacitinib 15 mg QD group in AE rate per 100 patient-years (refer to [Appendix B](#)).

10.2.2.2 Adverse Events Rates per 100 Patient-Years of Study Drug Exposure by SOC and PT

For the Any Upadacitinib 15 mg QD treatment group, the TEAE rate per 100 patient-years of exposure as outlined in Section [10.2.2.1](#) will be calculated overall, for each SOC and each PT, for each of the following events:

- All TEAEs
- Treatment-emergent serious adverse events (SAEs)
- Treatment-emergent severe adverse events
- TEAEs reasonably possibly related to study drug
- TEAEs leading to discontinuation of study drug
- TEAE leading to death

10.2.2.3 Adverse Events of Special Interest Rates per 100 Patient-Years of Study Drug Exposure

The Adverse Events of Special Interest (AESI) categories will be summarized and presented for the Any Upadacitinib 15 mg QD treatment group using SOC and MedDRA PT (for adjudicated cardiovascular events, the CAC adjudicated categories will be used).

The AESI categories will be identified per Standard MedDRA Queries (SMQs)/Company MedDRA Queries (CMQs).

The Adverse Events of Special Interest (AESI) rate per 100 patient-years of exposure as outlined in Section 10.2.2.1 will be calculated overall, for each SOC and each PT, for each of the AESI listed in Section 10.2.1.6.

10.2.2.4 Listing of Serious Adverse Events (Including Deaths) and Adverse Events Leading to Study Drug Discontinuation

All serious adverse events (SAEs), deaths, and adverse events leading to discontinuation of study drug will be listed.

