Appendix B. EAER and Normal Approximation Based 95% Confidence Interval

Assume the occurrence of TEAE of special interest follows a Poisson distribution and let λ denote the rate of occurrence of TEAE under the total exposure time for a treatment group. Let n be the number of AEs reported in Any Upadacitinib 15 mg QD group. Let T be the total number of days exposed to study drug summed across all treated subjects in Any upadacitinib 15 mg QD group. Under the assumption that n follow Poisson distribution with parameters λT , the $\hat{\lambda} = n/T$.

Using normal approximation, the 95% confidence interval can be calculated by (Liu GF, et al. 2006.):

$$\hat{\lambda} \pm Z_{\alpha/2} \hat{\sigma}$$

Where $\hat{\sigma} = \sqrt{\frac{n}{T^2}}$

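### Long-term adverse event rates count events up to 30 days after the last dose but divide by exposure that ends at the last dose

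*SAP*

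**What the plan says.** **Events.** SAP Section 10.2 counts an adverse event as treatment-emergent from the first dose to "no more than 30 days of the drug after the last dose of study drug". Protocol Section 8.1.5.2.1 sets the same limit: "AEs starting more than 30 days following the last dose of study drug will not be included in summaries of TEAEs".

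**Person-time.** SAP Section 10.2.2 states that "the denominator will be the total exposure time among subjects under the treatment group". Section 10.2.2.1 lists what the table shows: "The number of TEAEs reported, the total number of years of study drug exposure, and the TEAE rate per 100 patient-years". Section 8.1 defines the exposure: "Exposure to upadacitinib and placebo is defined as last dose date minus first dose date plus 1 day". Appendix B builds the confidence interval on the "total number of days exposed to study drug summed across all treated subjects". No section adds 30 days to any of these.

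**Which events belong to the group.** SAP Section 10.2.2 assigns events by the treatment received when they occur and adds: "This includes AEs occurred under Upadacitinib 15 mg QD exposure from subjects starting on Upadacitinib 15 mg QD", together with placebo switchers. It does not say whether the 30 days after the last dose count as being under exposure.

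**Data cut.** For the Week 104 analysis, SAP Section 4.5 says: "Safety analysis will include data collected up to Week 104 or premature discontinuation for every subject". It does not say whether discontinuation is of study drug or of study participation, although SAP Section 7.0 tabulates the two separately. The next paragraph of Section 4.5 provides for an updated long-term safety analysis at the final lock and states no such cut.

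**The concern.** A rate per 100 patient-years needs events and person-time from the same interval. Here the event interval can be up to 30 days longer per subject than the exposure interval. Any event in that tail raises the rate without raising the denominator. The SAP names the exposure-adjusted event rate as the main approach for long-term adverse events, so the mismatch runs through the overall, SOC, preferred-term and special-interest tables.

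The excess is largest, relative to exposure, for subjects who stop early. The design produces such subjects: from Week 24, non-responders on ASAS 20 at two consecutive visits are taken off study drug. The tail data will exist, because Protocol Section 6.1.4 collects adverse events for 30 days after stopping, and for longer in subjects who stay in the study.

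The wording also leaves room for different programs. One analyst may count all treatment-emergent events under Section 10.2. Another may drop tail events because of the under-exposure phrase in Section 10.2.2 or the cut in Section 4.5. The two would report different rates from the same data.

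**Working it through.** The SAP gives no figure to reproduce, so the check is to size the mismatch.

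**Inputs**
- 85 subjects per arm, 170 in total (SAP Section 4.2).
- Planned upadacitinib exposure to Week 104: 104 × 7 = 728 days for subjects starting on upadacitinib; 90 × 7 = 630 days for placebo subjects switching at Week 14.
- Tail: up to 30 days per subject (SAP Section 10.2).
- Assumption: the event rate in the tail equals the on-drug rate.
- Assumption for dropout: a fraction f of subjects stops halfway through planned exposure, with f from 10% to 40%. The documents give no long-term discontinuation rate.

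**Formula.** Let r be the event rate, T the exposure and L the tail time whose events are counted. Expected events are r × (T + L). The reported rate is r × (T + L)/T, so the relative overstatement is L/T.

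**No dropout, every tail counted**
- T = 85 × 728 + 85 × 630 = 115,430 days; divided by 365.25 this is 316.0 patient-years.
- L = 170 × 30 = 5,100 days = 14.0 patient-years.
- L/T = 5,100/115,430 = 4.4%. The matched denominator is 330.0 patient-years, and an event with a constant rate of 50 per 100 patient-years would be reported as 52.2.

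**With dropout.** T becomes 115,430 × (1 − f/2). L is 170 × f × 30 if only early stoppers have a counted tail, and 5,100 days if everyone has one.

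| f | Patient-years | Early stoppers' tails only | All tails |
|---|---|---|---|
| 10% | 300.2 | 0.5% | 4.7% |
| 20% | 284.4 | 1.0% | 4.9% |
| 30% | 268.6 | 1.6% | 5.2% |
| 40% | 252.8 | 2.2% | 5.5% |

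As one line of the table in full: at f = 40%, T = 115,430 × 0.8 = 92,344 days. Early stoppers' tails are 170 × 0.4 × 30 = 2,040 days, giving 2,040/92,344 = 2.2%. All tails give 5,100/92,344 = 5.5%.

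**Which column applies.** A Week 104 cut removes the tails of completers, so the third column is the relevant one for that analysis, provided early stoppers' tails are kept. The last column needs a data cut that includes everyone's tail, which could happen only at the final lock.

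**Section 4.5 beside Section 10.2**
- If discontinuation means study drug, the cut removes early stoppers' tails and Week 104 removes completers' tails. Events and exposure then largely coincide, but events that Section 10.2 defines as treatment-emergent are left out of the Week 104 analysis.
- If it means study participation, subjects who stop drug and stay in the study keep their tail events, and the mismatch remains for them.

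**The case against.** The strongest reply is that this is minor and in part already handled. The long-term rates cover one group, so no treatment contrast is affected, and the Period 1 comparison in SAP Section 10.2.1 uses percentages of subjects, not exposure rates. The bias overstates risk. Event counts and patient-years are both displayed, so a reader can see the denominator. All of that stands, and it limits the weight of the point. The under-exposure phrase in Section 10.2.2 does not answer it: that phrase leaves the tail undefined, and reading it as an exclusion would conflict with the treatment-emergent counts in Section 10.2.2.1.

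Three stronger readings are tempting, and the documents do not support them.
- *That Section 4.5 adds to the mismatch.* Read as drug discontinuation, it would shrink the mismatch at Week 104. It is a separate ambiguity.
- *That long-term rates are inflated by tens of percent.* A subject who stops after 98 days has a tail of 30/98 = 30.6% of exposure, but that is a ratio for one subject. The reported rate pools all events and all exposure. Even 4.4% assumes no dropout with every tail counted, which a Week 104 cut would largely exclude. At the final lock, subjects in five countries have dosed beyond Week 104, which lengthens exposure and lowers the percentage.
- *That serious late events are lost.* The omission follows only from the drug-discontinuation reading, and the final lock updates the safety analysis without that cut. The lung cancer in Protocol Section 3.2 came from an earlier programme and is timed from a final scheduled visit, not from an early last dose, so it shows nothing about this rule.

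It is also fair to say that adding off-drug days to the denominator changes what the rate means and could dilute it.

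**Conclusion.** The mismatch is in the text: the event window is up to 30 days longer per subject than the exposure window, and nothing reconciles them. Under equal event rates in the tail and on drug, the pooled overstatement is about 0.5% to 2.2% with only early stoppers' tails counted, and about 4.4% to 5.5% with all tails counted. The dropout part of these ranges rests on an assumed 10% to 40% stopping halfway. If the tail rate is k times the on-drug rate, the percentages scale by k. For a special-interest category with few events, a single tail event can move the rate by more than this average.

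The point concerns the definition of a descriptive safety measure. It does not touch efficacy or any between-arm safety comparison. The ambiguity in Section 4.5 is a second, separate item: it decides which early stoppers' events reach the Week 104 analysis.

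**What to change.** In SAP Section 10.2.2 and Appendix B, choose one of these and state it:
1. Use one window for both events and patient-years, from the first upadacitinib dose to the earliest of last dose + 30 days, death, end of follow-up or data cut-off.
2. Keep on-drug exposure as the denominator, say that the tail is left out on purpose, and add a rate that counts only events up to the last dose.

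Option 1 means the patient-years include some off-drug time and must be labelled so, because the tables are now titled per patient-years of study drug exposure. Option 2 leaves the main tables unchanged. State the same window for the first-event incidence rates that Section 10.2.2 plans for special-interest events.

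Separately, in Section 4.5, say whether premature discontinuation means study drug or study participation, and reconcile it with Section 10.2. Treatment-emergent events within 30 days of an early last dose, and on or before the data cut-off, should be included. Subjects still dosing after Week 104 should be cut at Week 104 for that analysis.

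The cost is wording in three places and one derived end date for option 1, or one extra set of rates for option 2. No new data are needed.
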